10.2.3 Subject Unique Identification Process

Each subject that signs a consent form is assigned a unique identification number by the ALCMI Data Repository. An example of a unique identifier is as follows: 011-01-001. The first number "011" is the ALCMI protocol number; the second number "011" is the site number; the third number "001" is the subject number. This identifier will be used for the purposes of the study only, and will be distinct from the patient identification (e.g. medical records number) noted on any medical record.

10.2.4 Confirmation of Enrollment

Once inclusion/exclusion criteria are verified, the study coordinator will notify the subject of their enrollment into the study. Subjects will be provided a study packet through the mail that will include an introduction letter (Appendix A), a signed copy of the consent form, a study questionnaire (Appendix B) a blood collection kit, and blood collection and handling instructions (Appendix C). Additionally, the subject's treating physician will be sent a letter (Appendix E) describing the study and informing them of their patient's participation in the study.

10.2.5 California-based Subjects

Subjects residing in California will be required to sign the California Bill of Rights at the time of confirmation of study enrollment. The study coordinator will provide the document during the initial introductory email.

10.3 BASELINE PLASMA COLLECTION

The study coordinator will coordinate the shipment of the plasma collection kit for the baseline draw within 4 days of enrollment confirmation. The plasma collection kit consists of a box with the required collection tubes and instructions for adequate acquisition, handling and shipment (Appendix C). A total of forty (40) mLs of blood will be collected for CLIA testing and storage for research purposes. The specimen will be

**Title: Study of Plasma Next Generation Sequencing for Remote Assessment,
Characterization, Evaluation of Patients With ALK Drug Resistance (**SPACEWALK**)**

either drawn at the time of other clinical blood work or a separate blood draw will be performed. Twenty (20) mLs of the collected blood specimens will be tested in a panel of somatic alterations in cfDNA by Resolution Bioscience. Twenty (20) mLs of the collected blood will be stored at the ALCMI Biorepository for future lung cancer research. See the ALCMI-011 Laboratory Guidelines for details on biospecimen shipping and handling.

10.3.1 Baseline Plasma NGS

The forty (40) mLs of blood will be shipped directly to Resolution Bioscience's CLIA certified laboratory for analysis as per the standard processes. Laboratory staff will be blinded as to the subject's treatment history.

The results of plasma genotyping will be reported to the subject and the subject's primary treating physician. Resolution Bioscience will also release the results to the study team for inclusion in ALCMI's data repository.

The plasma NGS report will not include any specific treatment recommendations but will describe the presence of an ALK rearrangement, ALK resistance mutation, or other relevant mutations using language such as the following:

- If plasma NGS assay is negative for ALK rearrangement and negative for an ALK resistance mutation, this suggests levels of tumor DNA which are inadequate for detection of resistance mechanisms.
- If plasma NGS assay is positive for ALK rearrangement and negative for an ALK resistance mutation, this makes it difficult to predict sensitivity to alternate ALK inhibitors.
- If plasma NGS assay is positive for an ALK resistance mutation, the expected sensitivity and resistance of this ALK mutation to alternate ALK inhibitors will be provided. For example, the ALK resistance mutation G1202R confers resistance to crizotinib, ceritinib and alectinib while is sensitive to lorlatinib and there are controversial results regarding brigatinib activity. These will be expressed in the report using language such as: *Likely resistant to crizotinib, ceritinib and alectinib. Possible sensitivity to brigatinib. Likely sensitive to lorlatinib.* Appropriate scientific references will be provided.

10.4 STUDY QUESTIONNAIRE

A study questionnaire (Appendix B) will be emailed to the subjects after enrollment to obtain information about the subjects' demographics, current condition, cancer history, and exposure history. The purpose is to gain information about the subject that may or may not be included in their medical records, but will allow the study staff to obtain a more complete representation of the patients' cancer history.

10.5 CLINICAL DATA COLLECTION

A brief interview with the subjects and a review of the medical records provided will be completed for those selected for entry into the study. Data will be entered on the appropriate CRF in the ALCMI Data Repository. A CRF must be completed for each subject who has been enrolled and has signed an informed consent, including those that fail the screening process or are discontinued from the study. The following clinical data will be collected:

- Demographic data: age at diagnosis, age at enrollment, race/ethnicity, smoking history

**Title: Study of Plasma Next Generation Sequencing for Remote Assessment,
Characterization, Evaluation of Patients With ALK Drug Resistance (**SPACEWALK**)**

- Cancer characteristics: pathology, sites of metastatic disease, prior genotyping results
- Cancer history: date of diagnosis, date of advanced disease
- Treatment history: dates of previous surgery, radiotherapy, chemotherapy and targeted therapy

10.6 RADIOLOGY IMAGE COLLECTION & ANALYSIS

To characterize tumor response and study patient outcomes, CT images from subjects will be collected by the study staff and transferred to the Laboratory for Computational Imaging Analysis at Columbia University. This will be an exploratory analysis as we cannot control the quality and timing of these scans. This imaging analysis will complement the plasma response analysis.

Study staff will assist in obtaining copies of CT scans. For study staff to request copies of CT scan, study participants will be asked to complete a release form allowing their records to be obtained. The study staff will obtain the CT scans for all subjects and the release forms will be maintained in a locked filing cabinet. Up to 25 CT scans will be collected per subject, depending upon availability. PHI embedded in the images will be de-identified by the Laboratory for Computational Imaging Analysis at Columbia University prior to analysis. Using computer-aided-diagnosis software, each scan will be assessed. When serial imaging is available, change in nodule size will be characterized. Because each scan will already have undergone clinical review, no findings from the CT image analysis will be reported back to the subject.

10.7 ARCHIVAL TISSUE COLLECTION

On a case by case basis, the study team may seek archival tissue specimens from subjects to better understand novel or conflicting liquid biopsy results, we may need to request prior biopsy tissue to perform somatic tumor sequencing. Subjects do not need a biopsy to participate in this study. When available, ten (10) slides and one (1) H&E slide will be collected from an archived specimen stored at the subject's treating institution. Tumor specimens will be labelled with the Subject Identification Number and any genomic analysis will be considered investigational, with no results returned to the subject.

10.8 FOLLOW-UP

After enrolled into the study, the study coordinator will contact the subject weekly for 4 weeks, or as the study coordinator deems necessary per the subject's treatment plan. The purpose of the study-specific Follow-Up Visit is to document any new treatment initiation and to release the optional plasma collection kit (see section 10.9), if applicable. It is expected that at least two but no more than four study-specific Follow-Up visits will occur in the first 12 weeks.

Subjects will then be contacted every 3 months, from the date of enrollment, to obtain information about therapy outcome until treatment failure. Treatment failure will be defined as either termination of the current treatment or initiation of a new systemic therapy. Subjects will be followed every three months for a maximum of 2 years post enrollment or until death.

10.9 OPTIONAL RESPONSE PLASMA COLLECTION

An optional blood collection will be offered 1-3 weeks but no more than 8 weeks after initiation of the subject's post-enrollment anticancer regimen. The subject will be asked to notify the study coordinator when they have initiated a treatment regimen. Upon notification, the study coordinator will coordinate the

**Title: Study of Plasma Next Generation Sequencing for Remote Assessment,
Characterization, Evaluation of Patients With ALK Drug Resistance (**SPACEWALK**)**

shipment of the plasma collection kit and a letter (Appendix F) describing the purpose of the optional blood collection to the subject.

The plasma collection kit consists of a box with the required collection tubes and instructions for adequate acquisition, handling and shipment (Appendix C). The blood draw will occur at the subject's next standard of care blood draw. The collection time schema allows a window of +/- 2 weeks from the specified date. A total of twenty (20) mLs of blood will be collected for research purposes. Specimens will be labeled with the subject's unique identification (no PHI), shipped directly to the ALCMI Biorepository and stored for future research. See the ALCMI-011 Laboratory Guidelines for details on biospecimens shipping and handling.

10.10 OPTIONAL PROGRESSION PLASMA COLLECTION

An additional optional blood collection will be offered after progression on the subject's post-enrollment antitumoral regimen. The subject will be asked to notify the study coordinator when they have progressed on their treatment regimen. Upon notification, the study coordinator will coordinate the shipment of the plasma collection kit and a letter (Appendix G) describing the purpose of the optional blood collection to the subject.

The plasma collection kit consists of a box with the required collection tubes and instructions for adequate acquisition, handling and shipment (Appendix C). The blood draw will occur at the subject's next standard of care blood draw. The patient is eligible for a progression blood draw at any time after clinical determination of disease progression (by their treating physician) and before initiating a subsequent line of therapy. A total of twenty (20) mLs of blood will be collected for research purposes. Specimens will be labeled with the subject's unique identification (no PHI), shipped directly to ALCMI's biobank and stored for future research. See the ALCMI-011 Laboratory Guidelines for details on biospecimens shipping and handling.

Up to two optional progression plasma specimens will be collected upon progression on two different lines of therapy. This allows us to explore sequential therapy in case an initial therapy is ineffective but a subsequent therapy is effective, both suited in the same patient.

Title: Study of Plasma Next Generation Sequencing for Remote Assessment, Characterization, Evaluation of Patients With ALK Drug Resistance (SPACEWALK)

10.11 STUDY CALENDAR

Table 1: Times showed are estimations and can be adjusted with Principal Investigator approval if needed pending specific subject circumstances.

Visit Schedule	Registration, Enrollment and Visit 1 - Blood Collection		Follow-up Visits 2-5	Follow-up Visits 6-12	Visit 13/End of Study/Early Termination
	Screening ¹	Blood Collection	Up to 4 visits within 12 week window ⁴	Every 3 months from Enrollment ⁷ Visit 6 (+1 month) Visits 7-12 ±1 Month	Study end ³ 24 months -1 Month ⁷
Informed consent	x				
Registration	x				
Review inclusion & exclusion criteria	x				
Baseline blood collection kit		x			
Request medical records & imaging results	x			x ⁶	
Follow-up ⁴			x ⁴	x	x
Receive NGS report			x ⁵		
Send kit for optional blood draw			x ²	x ²	x ²

¹ Screening is permitted to extend as long as 30 days, if necessary.

² Optional blood specimens may be collected 1-3 weeks after initiation of a new therapy as well as when a subject's disease progresses on that therapy, prior to initiating subsequent line of therapy.

³ Subjects will be followed on study for a minimum of 8 months and for a maximum of 24 months if the study remains open or in follow-up, or until death.

⁴ Subjects weekly for 4 weeks, or as necessary per the subject's treatment plan. It is expected that at least two but no more than four study-specific Follow-Up visits will occur in the first 12 weeks.

(Visit 2 Week 1 ±3 days, Visit 3 Week 2 ±3 days, Visit 4 Week 3 ±3 days, Visit 5 Weeks 4-12)

⁵ The NGS Report is only received once during the 12 week follow-up, typically within 14 days.

⁶ Medical records & imaging results are only requested if attempts to reach the subject for follow-up have been unsuccessful, otherwise, data captured on disease progression and treatment changes are subject-reported.

⁷ 3 month visit windows include Visit 6 (3 months +1 month), Visits 7-12 (6,9,12,15,18,21 months ±1 month), Visit 13 (24 months -1 month)

Title: Study of Plasma Next Generation Sequencing for Remote Assessment, Characterization, Evaluation of Patients With ALK Drug Resistance (SPACEWALK)

11 COMPENSATION

There will be no compensation or incentives offered to the subject.

Research blood draws will be performed with standard of care laboratories whenever possible. Subjects will be reimbursed for reasonable costs associated with research-only blood draws upon receipt of an invoice.

12 STATISTICAL CONSIDERATIONS

12.1 STUDY DESIGN & ENDPOINTS

A total of 300 subjects will be enrolled. Of those, we assume approximately 53% of the subjects (n=160) will have DNA shed and detectable ALK rearrangements, and will have progressed on either alectinib or ceritinib. Of the 160 subjects, we assume 80 subjects will have progressed on alectinib and 80 subjects will have progressed on ceritinib. Table 1 below shows the expected distribution of resistance mutations among these subjects.

Table 1: Expected distribution of resistance mutations

ALK mutation	Frequency after ceritinib	Frequency after alectinib
C1156Y	5%	0%
F1174X	15%	0%
I1171X	0%	10%
L1196M	0%	5%
G1202R	20%	30%
G1202del	5%	5%
D1203N	2%	0%
L1198F	5%	0%
C1156Y + L1198F	2%	2%
F1245C	0%	2%
No mutation	46%	46%

We will focus on two key mutational differences, F1174X and I1171X. With a type I error of 0.10, we have 99.8% power to detect the shown difference in acquiring the F1174X mutation, and 95.3% power to detect the shown difference in acquiring the I1171X mutation.

We will investigate response and time to treatment discontinuation (TTD) of those patients who have acquired an ALK mutation on their respective potential targeted therapy.

Table 2 below summarizes the maximum width of a 90% exact binomial confidence interval for response (CR+PR) to potential targeted therapy, per ALK mutation status.

Title: Study of Plasma Next Generation Sequencing for Remote Assessment, Characterization, Evaluation of Patients With ALK Drug Resistance (SPACEWALK)

Table 2: Max Width of 90% Exact Binomial Confidence Interval

ALK mutation	Total Sample Size	Number of Responses	Max Width of 90% CI
C1156Y	4	2	0.8043
F1174X	12	6	0.5093
I1171X	8	4	0.6143
L1196M	4	2	0.8043
G1202R	40	20	0.2779
G1202del	8	4	0.6143
D1203N	2	1	0.9491
L1198F	4	2	0.8043
C1156Y + L1198F	4	2	0.8043
F1245C	2	1	0.9491

TTD is defined as the time from treatment start to treatment discontinuation for any reason, including disease progression, unacceptable toxicity, or death. For subjects who are alive without discontinuation, follow-up will be censored on the date of last adequate disease assessment. Table 3 below summarizes the intended TTD hazard ratios, median TTD improvement from 5 months, assuming exponential event time, power, and number of TTD events at full information with a Type I error of 0.10, for a total sample size of 10 or 20 subjects. TTD will be estimated using the Kaplan-Meier method and Cox proportional hazards models will be used to estimate hazard ratios. Comparisons of groups will be made using the log-rank test and Cox modeling.

Table 3: Time to Treatment Discontinuation

Total Sample Size	Number of events	Hazard Ratio	Median Survival	Median Survival After Therapy	1-Sided Type I Error Rate	Power
10	6	0.45	5 Months	12.5 Months	0.10	83%
20	14	0.50	5 Months	10 Months	0.10	89%

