5.5 PLASMA RESPONSE

Plasma response can also be assessed quantitatively through serial measurement of plasma genotyping. This phenomenon has been better studied in patients with advanced EGFR-mutant NSCLC. For example, a translational analysis assessing EGFR mutant copies in plasma ctDNA was done within the FASTACT-2 study. This was a randomized, double-blind, Phase III study of intercalated erlotinib or placebo with chemotherapy followed by maintenance erlotinib or placebo in previously untreated advanced NSCLC patients²¹

[figure not shown]

Figure 1. Dynamic change in EGFR mutant cfDNA at baseline, cycle 3, and progression (PD). GC+E, erlotinib plus chemotherapy; GC+P, placebo plus chemotherapy. ^aCopy/mL 0.1 were undetectable²¹.

In the subset of patients with EGFR mutations there was a strong correlation between the dynamics of EGFR mutations detected in cfDNA and the radiologic assessment performed at cycle 3 and at progression (**Figure 1**). The same approach is now feasible for ALK mutations with current available plasma NGS assays and could be now done in ALK positive NSCLC patients²². Furthermore, studies of plasma genotyping performed by Sacher and colleagues and as part of the AURA trial support that decreases in EGFR mutant clones in plasma ctDNA correlate with higher tumor responses while persistence or increase correlate with treatment failure (**Figure 2**).^{23, 24}

[figure not shown]

Figure 2. PFS based on clearance or detection of EGFR mutations in plasma samples taken A) 3 weeks and B) 6 weeks post initiation of osimertinib.²³

Those changes can be found in plasma early after treatment initiation and before the first tumor assessment usually done after 6-8 weeks on treatment. In ALK-mutated lung cancers, we expect to observe a similar phenomenon in which levels of ALK mutant clones will decrease in lung cancers exhibiting higher tumor responses.

Title: Study of Plasma Next Generation Sequencing for Remote Assessment,
Characterization, Evaluation of Patients With ALK Drug Resistance (**SPACEWALK**)

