7.2 SECONDARY OBJECTIVES

- To study the feasibility, sensitivity, and turnaround time of plasma NGS in lung cancer patients with ALK TKI resistance.
- To study the outcomes of patients with ALK TKI resistance depending upon resistance mechanism detected and subsequent therapy received.
- To study the relationship between plasma NGS results from plasma specimens to advanced ALK positive NSCLC subjects on progression to a next generation ALK TKI and treatment decisions.
- To explore the ability of plasma genotyping to identify novel ALK resistance mechanisms.

Title: Study of Plasma Next Generation Sequencing for Remote Assessment,
Characterization, Evaluation of Patients With ALK Drug Resistance (SPACEWALK)

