8 STUDY DESIGN

8.1 REMOTE CONSENT & PLASMA NGS

Our overarching hypothesis is that we can conduct a remote consent study using plasma NGS to characterize ALK resistance mechanisms arising in ALK positive NSCLC patients with progression while on a next generation ALK TKI, and that the chances of response to further treatment with a different ALK TKI can be predicted using those plasma NGS results.

This study will attempt to prospectively assess the resistance mechanisms detected by a plasma NGS assay in patients with advanced ALK positive NSCLC and systemic progression outside the brain using a web-based remote consent form process. Subjects will be sent blood collection kits with the necessary materials for local draws and those specimens will be sent directly by the subjects to the central laboratory (Resolution Bioscience) for plasma NGS. Plasma NGS results will be returned to the subject, their treating physician and study team, aiming to be returned within 2 weeks by Resolution Bioscience. This will allow prospective characterization of ALK resistant mutations arising in subjects after progression on different specific ALK TKIs. In addition, subsequent treatments and radiologic assessments received by the subjects will be prospectively monitored. A correlation between the ALK resistance mechanisms present at baseline, treatments received before and after plasma NGS assessments and outcomes will be analyzed.

We further propose here that plasma NGS could grant the ability to non-invasively detect specific ALK resistance mutations and, therefore, predict the sensitivity to different ALK TKIs and patients' outcomes. However, prospective CT-based response assessment is not feasible with a remote participation approach. We will instead use time to treatment discontinuation (TTD) as an alternate outcome. In collaboration with the US Food and Drug Administration (FDA), we found that TTD closely correlates with PFS outcomes in patients with genomic-driven lung cancer treated targeted therapies (manuscript in development), and is thus, well suited for studies of real-world evidence like ours. As such, we propose to evaluate the next treatment received by the subjects using TTD as the a time endpoint to assess treatment benefit. We also plan to analyze if plasma NGS results have any impact on the treatment decision process and if alterations in other relevant genes can impact subjects' outcomes.

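### TTD counts stopping treatment for any reason but censors ongoing subjects at an undefined disease assessment, which can discard known on-treatment time and shorten TTD

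*Combined protocol and SAP*

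**What the plan says.** Section 12.1 runs TTD from treatment start to discontinuation for any cause, naming progression, toxicity and death. The censoring rule for everyone else is: "For subjects who are alive without discontinuation, follow-up will be censored on the date of last adequate disease assessment". Adequate disease assessment is not defined, and no rule covers a subject who has none. Kaplan-Meier, log-rank and Cox analyses are planned.

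Four other places bear on whether that date will exist:

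- Section 8.1 adopts TTD because "prospective CT-based response assessment is not feasible with a remote participation approach".
- Section 10.8 sets the source of treatment status: "Subjects will then be contacted every 3 months, from the date of enrollment, to obtain information about therapy outcome until treatment failure".
- Section 10.6 states "The study staff will obtain the CT scans for all subjects", but also "This will be an exploratory analysis as we cannot control the quality and timing of these scans".
- Footnote 6 of the calendar in section 10.11 states "Medical records & imaging results are only requested if attempts to reach the subject for follow-up have been unsuccessful"; otherwise progression and treatment changes are reported by the subject.

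TTD serves a secondary objective in section 7.2: "To study the outcomes of patients with ALK TKI resistance depending upon resistance mechanism detected and subsequent therapy received".

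**The concern.** The event and the censoring date belong to different endpoints. Censoring at the last assessment suits progression, which can be seen only at an assessment. Stopping a drug is known from a phone call.

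Take two subjects whose last assessment was at month 9. One stops treatment at month 18 and contributes an 18-month event. The other is confirmed on treatment at month 18 and is censored at month 9. The second loses nine months of known time at risk only because no event occurred. Censoring then depends on the outcome, and the planned methods assume that it does not.

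Two consequences follow. TTD is shortened, and more so where TTD is long, because more subjects are then ongoing. Comparisons by mutation or therapy are also distorted. With similar capture in the groups, differences shrink. With unequal capture, they can shrink or widen.

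The rule also brings back the dependence on scans that TTD was chosen to avoid. Under footnote 6, the ongoing, reachable subject is the one whose follow-up imaging is not requested.

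**Working it through.** **Inputs from the plan.** Section 12.1: exponential TTD, reference median 5 months, one-sided type I error 0.10, and Table 3 (20 subjects, 14 events, median 10 months, power 89%; 10 subjects, 6 events, median 12.5 months, power 83%). Section 12.2: 24 months of accrual, follow-up of at least 8 and at most 24 months.

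**Assumptions.** Uniform accrual, so follow-up is C = min(24, U(8, 32)) months. The lag between enrollment and treatment start is ignored. Assessment intervals and capture shares are not in the documents and are varied.

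**1. Table 3 reproduced.** One-sample exponential test: power = Φ(√d·|ln HR| − 1.2816).
- 20 subjects: √14 × 0.6931 − 1.2816 = 1.312, power 90.5% (exact gamma version 89.9%), against 89% stated.
- 10 subjects: with HR 5/12.5 = 0.40, √6 × 0.9163 − 1.2816 = 0.963, power 83.2%, as stated. The printed HR of 0.45 gives 75.0%; that inconsistency is a separate matter.

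**2. Share still on treatment.** With λ = ln 2/median, P(ongoing) = (e^(−8λ) − e^(−24λ))/(24λ) + e^(−24λ)/3.
- Median 10: (0.574 − 0.190)/1.664 + 0.190/3 = 0.231 + 0.063 = 29%.
- Medians 5 and 12.5: 10% and 37%.
- Expected events: 20 × 0.706 = 14.1 and 10 × 0.629 = 6.3, matching the 14 and 6 in Table 3. The follow-up model therefore fits the plan.

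**3. How the rule acts.** Events keep their full time; ongoing subjects lose the gap since their last assessment. For a true median of 10, expected time at risk per subject is 0.706/0.0693 = 10.19 months. Suppose scans are 3-monthly and half are captured. The mean loss is then 4.03 months in the 29.4% ongoing, or 1.19 months per subject. The event rate is inflated by 10.19/(10.19 − 1.19) = 1.13, so a true ratio of 0.50 against a fixed 5-month reference becomes 0.57.

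**4. Kaplan-Meier medians and Cox hazard ratio.** Medians were solved numerically. The hazard ratio is for 10 against 5 months, simulated with 400,000 per group and the same capture in both.

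| Censoring of ongoing subjects | True 5 | True 10 | True 12.5 | HR (true 0.50) |
|---|---|---|---|---|
| No loss | 5.00 | 10.00 | 12.50 | 0.499 |
| Gap up to 3 months | 5.00 | 9.83 | 12.15 | 0.502 |
| Gap up to 6 months | 4.98 | 9.58 | 11.75 | not run |
| Gap up to 8 months | 4.95 | 9.40 | 11.47 | 0.512 |
| One 6-8 week scan only, 25% | 4.87 | 9.10 | 11.07 | 0.523 |
| One 6-8 week scan only, 50% | 4.74 | 8.24 | 9.72 | 0.556 |
| One 6-8 week scan only, 100% | 4.48 | 6.68 | 7.28 | 0.671 |
| Time 0, 25% | 4.82 | 8.98 | 10.92 | 0.528 |
| Time 0, 50% | 4.65 | 8.02 | 9.44 | 0.568 |
| Time 0, 100% | 4.31 | 6.28 | 6.80 | 0.702 |

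The 6-8 weeks come from section 5.5, which gives the usual time of the first assessment. Taking it as the only one, or censoring at time 0 where there is none, is an assumption.

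**5. Unequal capture.** With 50% of ongoing subjects censored at time 0 in one group only, the hazard ratio becomes 0.436 if that is the short-TTD group and 0.650 if it is the long-TTD group.

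**6. Power against a fixed 5 months.** In simulation with correct censoring, power is about 92% (20 subjects) and 87% (10 subjects). With 3-monthly scans and 100%, 50%, 25% or 0% captured, it becomes 90%, 83%, 66% or 5%, and 85%, 78%, 62% or 5%.

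**7. The alternative rule.** Censoring at the last 3-monthly contact returns medians of 5.0, 9.9 and 12.6 for true values of 5, 10 and 12.5.

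**The case against.** The text says disease assessment, not scan. Section 8.1 rules out prospective CT-based response assessment, and footnote 6 makes progression and treatment changes subject-reported. The quarterly contact could therefore be the intended assessment, and the bias would nearly vanish. That reading is possible, but the plan does not state it, and two analysts could derive different censoring dates from the same data.

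The large figures are stress tests. Time-0 censoring is a supplied rule, the 100% rows sit badly with section 10.6 obtaining scans for all subjects, and nothing in the plan suggests that capture differs by mutation or therapy. This stands, and those rows should be read as bounds. Footnote 6 nevertheless makes incomplete capture plausible.

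At the planned sizes sampling error dominates. With 20 subjects, a true median of 10 and correct censoring, the 5th to 95th percentile range of the estimated median is about 5.3 to 16.3 months, so a shift to 9.4-9.8 is small. This is also true, but the bias is systematic and avoidable at almost no cost.

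**Conclusion.** The concern holds. The censoring rule does not match the TTD event and, read literally, biases TTD short. The direction is certain wherever known on-treatment time is discarded; the size is conditional.

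- With assessments continuing to within 3 to 8 months of last follow-up, the effect is small: a true median of 10 becomes 9.8 to 9.4, and a hazard ratio of 0.50 becomes 0.50 to 0.51.
- If 25% to 50% of ongoing subjects have no usable on-treatment assessment and are censored at time 0, the median becomes 9.0 to 8.0 and the hazard ratio 0.53 to 0.57. The extreme case, all of them, gives 6.3 and 0.70.
- Unequal capture can move the hazard ratio either way, to 0.44 or 0.65 in the case examined.

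These figures rest on exponential TTD, uniform accrual and assumed capture shares. The primary objective is untouched. This should be fixed before analysis, but it does not threaten the study.

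**What to change.** In section 12.1, replace the censoring sentence with: *Subjects who have not discontinued are censored on the date they were last confirmed, by subject contact or medical record, to be receiving the index treatment.* Remove the reference to disease assessment from the TTD definition.

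Separately, reconcile section 10.6 with footnote 6 of the calendar on whether follow-up scans are collected for all subjects. This also bears on the response analysis in Table 2 and remains open after the TTD sentence is changed.

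The cost is one sentence and one clarification. No new data are needed, because the contacts in section 10.8 already provide the date.

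### Table 3 gives TTD power only for 10 and 20 subjects and ties neither size to a mutation group, while Table 2 expects 8 or fewer subjects in eight of ten groups

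*Combined protocol and SAP*

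**What the plan says.** Section 12.1 states that the study will examine response and "time to treatment discontinuation (TTD) of those patients who have acquired an ALK mutation on their respective potential targeted therapy".

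Table 2 then gives confidence interval widths "for response (CR+PR) to potential targeted therapy, per ALK mutation status". Its expected group sizes are C1156Y 4, F1174X 12, I1171X 8, L1196M 4, G1202R 40, G1202del 8, D1203N 2, L1198F 4, C1156Y + L1198F 4 and F1245C 2. They total 88.

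Table 3 gives TTD power "for a total sample size of 10 or 20 subjects", assuming exponential times and a 5-month reference median. Its columns include "Hazard Ratio Median Survival Median Survival After Therapy 1-Sided Type I Error Rate Power", and its two rows read "10 6 0.45 5 Months 12.5 Months 0.10 83"% and "20 14 0.50 5 Months 10 Months 0.10 89"%. The text beside the table adds: "Comparisons of groups will be made using the log-rank test and Cox modeling".

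The plan does not say which mutation, or which pooled set of mutations, the sizes 10 and 20 stand for. It gives no TTD power for 2, 4 or 8 subjects.

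**The concern.** Response gets a precision statement for each mutation. TTD, which Section 8.1 adopts as the measure of treatment benefit because CT-based response cannot be assessed prospectively, gets two power figures at sizes that match no row of Table 2. Eight of the ten groups are smaller than the smaller of those sizes. One of them is I1171X, which Section 12.1 singles out with F1174X as a key mutational difference.

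Without a link between the tables, nobody can tell which TTD analyses the plan considers adequately powered. A null TTD result in a group of 2 to 8 could later be read against a power of 83% or 89% that was never calculated for that group.

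**Working it through.** **Inputs.** From Table 3: one-sided type I error 0.10, exponential times, reference median 5 months, alternative medians 12.5 months (6 events in 10) and 10 months (14 events in 20). From Table 2: the group sizes. From Section 12.2: 24 months of accrual, with at least 8 and at most 24 months of follow-up per subject. Two assumptions are added: accrual is uniform, and treatment starts at enrollment.

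**Reproducing Table 3.** Take one group against a fixed 5-month median, with d events.
- Exact: power = P(χ²(2d) > HR × χ²₀.₉₀(2d)).
- Normal approximation: power = Φ(√d × |ln HR| − 1.2816).

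Row 1, using the ratio of the medians, HR = 5/12.5 = 0.40, and d = 6: exact P(χ²(12) > 0.40 × 18.549 = 7.420) = 82.9%; normal approximation 83.2%. Stated: 83%.

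Row 2, HR = 5/10 = 0.50, d = 14: exact P(χ²(28) > 0.50 × 37.916 = 18.958) = 89.9%; normal approximation 90.5%. Stated: 89%.

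Row 1 with its printed HR of 0.45 and d = 6 gives 75.7% exact and 75.0% approximate, so it does not reproduce 83%. Under exponential times a ratio of 0.45 corresponds to a median of 5/0.45 = 11.1 months, not 12.5.

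A two-group 1:1 comparison with the same total events, Φ(√(d/4) × |ln HR| − 1.2816), gives 38.1% (HR 0.45) or 43.7% (HR 0.40) for row 1 and 50.6% for row 2. Table 3 is therefore a one-sample calculation, not a log-rank comparison of two groups.

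**Event fractions.** With λ = ln 2/median and follow-up uniform on 8 to 32 months, cut at 24, the expected fraction is 1 − [(e^(−8λ) − e^(−24λ))/λ + 8e^(−24λ)]/24. This is 62.8% for a 12.5-month median and 70.5% for 10 months, in line with Table 3's 6/10 and 14/20.

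**Power at the Table 2 sizes.** Exact formula at the unrounded expected events, with the normal approximation in brackets:

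| n | Mutations | Events, 12.5 mo | Power, 12.5 mo | Events, 10 mo | Power, 10 mo |
|---|---|---|---|---|---|
| 2 | D1203N, F1245C | 1.26 | 44% (40%) | 1.41 | 36% (32%) |
| 4 | C1156Y, L1196M, L1198F, C1156Y + L1198F | 2.51 | 60% (57%) | 2.82 | 49% (45%) |
| 8 | I1171X, G1202del | 5.03 | 78% (78%) | 5.64 | 66% (64%) |
| 12 | F1174X | 7.54 | 88% (89%) | 8.47 | 78% (77%) |
| 40 | G1202R | 25.1 | over 99% | 28.2 | 99% (99%) |

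The figures for 2 and 4 subjects are only indicative. At n = 4 and a 12.5-month median, rounding the events to 2 or to 3 moves the exact power from 54% to 64%. The figures for n = 8 change little between methods. With the printed HR of 0.45 and 5 events, n = 8 gives 69% (normal approximation) to 71% (exact).

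**The case against.** The strongest reply is that Table 3 makes no false claim. It states its sample sizes and, unlike Table 2, is not labelled by mutation. The sentence introducing TTD could also cover pooled carriers. A reader might infer that the plan promises 83% or 89% for every mutation, but the documents do not say so. The defect is the missing link between the tables.

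A reader might also infer that a null TTD result would be worthless in eight of ten groups. That goes too far. The plan sets no power threshold, and 78% at n = 8 for the larger effect is close to the 83% stated for n = 10. F1174X and G1202R together hold 12 + 40 = 52 of the 88 expected carriers, so most carriers are in groups above 10.

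A third tempting step is to shrink the groups further by the 70% assay sensitivity in Section 5.3. The documents do not support it. Table 2 is built from the 160 subjects assumed to have detectable ALK rearrangements, and Section 5.3 uses a detected rearrangement as its quality control. A further 70% may count detection twice.

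Finally, TTD by resistance mechanism belongs to a secondary objective (Section 7.2), Table 3 does not set the enrollment of 300, and Table 2 already shows how small the groups are. This limits the consequence. It does not supply the missing link, and it does not resolve the inconsistency in row 1.

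**Conclusion.** The point holds as a gap in the TTD power statement. The two sizes in Table 3 are tied to no group, and eight of the ten groups in Table 2 fall below both. For I1171X, power is about 78% at a 12.5-month median and 66% at 10 months. F1174X has about 88% and 78%. G1202R exceeds 98% for either effect. Groups of 2 to 4 have roughly 40-60% and 32-49%, depending on the method.

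These figures rest on exponential times, uniform accrual, treatment starting at enrollment and a fixed 5-month comparator. The group sizes are expected carrier counts and so upper limits for TTD. The study is non-interventional (Section 14.2.9) and its report makes no treatment recommendations (Section 10.3.1), so not every carrier will receive the matched therapy. The documents give no uptake figure, and no reduction is applied here.

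Separately, row 1 of Table 3 contradicts itself: its medians and its 83% agree with a hazard ratio of 0.40, and the printed 0.45 agrees with neither.

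**What to change.** - Restate Table 3 at the Table 2 group sizes, with the event count for each and one hazard ratio per row that agrees with its medians. For row 1, either print 0.40 with 12.5 months, or keep 0.45 with about 11.1 months and power of about 75-76% at 6 events.
- State that the figures are for one group against a fixed 5-month median, and that they do not apply to the planned log-rank comparisons of groups.
- Name the groups for which TTD power is claimed: G1202R and, for the larger effect, F1174X. If pooling is intended, define the pooled set and its expected size.
- Report TTD in the smaller groups descriptively, with Kaplan-Meier estimates and 90% confidence intervals.
- Say that the sizes assume every carrier starts the matched therapy.

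The cost is a revised table and a few sentences. No subjects or procedures are added, but the stated power becomes less favourable for most mutations.
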